7.6 Withdrawal

Participants may withdraw from the study at any point. If this occurs, the reason for withdrawal if provided by the participant will be documented in the participant's CRF and the Study Recruitment log. Any study related identifiable information will be destroyed (not including the consent form). However, non-identifiable study information up to and including the point of withdrawal will be retained.

7.7 End of Study

End of study is defined as the final visit of the final participant. The study can be terminated by the investigators or sponsor at any time for clinical or administrative reasons.

7.8 Data Analysis

To investigate whether London Classification diagnoses differs when using the rectal barostat compared to elastic balloon distension, a binary indicator will be used to determine the percentage of patients who's diagnoses were in agreement. To examine this closer, a Fisher's exact test will be used to determine whether the difference in number of diagnoses between the elastic balloon distension and rectal barostat reaches a significance level of p=0.05.

To assess repeatability of sensory thresholds at first sensation, normal urge, and sustained urgency of the rectal barostat, an intraclass correlation coefficient will be calculated for each test.

To identify whether there is a correlation between total rectal capacity and the volume of the elastic balloon at the sensory threshold of sustained urgency, a Pearson's correlation will be calculated to test the strength of the relationship between these variables.

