Once sensory thresholds have been measured, a diagnosis of normal, rectal hypersensitivity, rectal hyposensitivity, or borderline hyposensitivity is made according to the London Classification disorders of rectal sensation^[11]. In this study we aim to identify whether patients receive the same diagnosis, according to the London Classification, regardless of whether the elastic balloon distension or rectal barostat is used. To achieve this, patients attending for their standard rectal sensitivity tests using the elastic balloon will be invited to repeat their study using the rectal barostat, and the diagnosis they receive (normal, hypersensitive, hyposensitive, borderline hyposensitive) will be compared. From this data, an indication of the clinical utility of the rectal barostat can be suggested, depending on whether a patient's diagnoses changes. As well as this, participants will be offered a questionnaire following their clinic appointment, which will include questions on their tolerability of each test, in order to gather information on the feasibility of a larger cohort study in the future.

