2.0 RATIONALE

A recent service evaluation was conducted to compare the number of diagnoses of disorders of rectal sensitivity (n=70 per site) across NUTH and CDDFT services, in order to identify whether both pieces of equipment produce similar proportions. In NUTH, the majority of patients (91.4%) were diagnosed as normal, whereas in CDDFT, the majority of patients (65.7%) were diagnosed with rectal hypersensitivity. This suggests a possible difference in how each piece of equipment classifies patients, although the limitations such as two different cohorts of patients being studied, and the relatively small sample size should be acknowledged. This service evaluation supported the need for more research into our normal values and how we assess rectal sensitivity, and questioned whether a rectal barostat could be more appropriate.

There is little research directly comparing the assessment of rectal sensitivity using elastic balloon distension and the rectal barostat. A study by Sauter et al. (2014) assessed 26 healthy volunteers using both the elastic balloon inflation and barostat methodologies to assess rectal sensitivities, by recording volume inflated at first sensation, normal urge, and

sustained urgency. They found there was no agreement between the elastic balloon and barostat recorded volumes, however, this is possibly due to the difference in physical properties and shape at identical volumes, which the study failed to take into account^[12]. There are currently no studies comparing the two devices in a symptomatic population, and no indication whether patients receive different diagnoses depending on what device is used to assess rectal sensitivity. Accurate and comprehensive assessment of disorders of rectal sensation to distension in symptomatic patients is vital, as studies have suggested patients with rectal hyposensitivity treated with biofeedback therapy improved their sensory thresholds and symptom severity^[14], and sensory retraining is of greater utility when treating faecal incontinence than strength training alone^[15].

This feasibility study will help investigate key variables required to inform a future definitive study, which will aim to determine whether patients receive a different diagnosis of rectal sensitivity dependent upon the test used. Moreover, a definitive study will address the potential impact of rectal sensitivity testing methodologies on patient outcomes.

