3.3 Outcome Measures

As this is a feasibility study, there are no primary outcome measures, only secondary outcome measures. These include:

- The London Classification diagnoses of each patient when rectal sensitivities are assessed using Laborie system elastic balloon distension versus the rectal barostat, and Medtronic system elastic balloon distension versus the rectal barostat.
- Percentage of rectal capacity at each sensory threshold per test will be measured to assess repeatability
- Total rectal volume (mL) measured using the rectal barostat will be recorded to assess correlation between capacity and balloon inflation (mL) at sustained urgency.
- The number of patients who were eligible to participate in the study.
- The number of patients who chose to participate in the study.
- The number of patients who dropped out of the study.
- The length of time required for the rectal barostat protocol and the elastic balloon distension protocol in clinic
- Costings of rectal barostat test comparison (costs of barostat bags and any additional staff time required)
- Study acceptability and tolerability assessment.

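### The agree/disagree percentage ignores how far and in which direction balloon and barostat diagnoses differ, and the added Fisher test recovers only an unpaired, unordered net shift

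*Protocol*

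**What the plan says.** Protocol section 1.0 (Background) names four possible results: "a diagnosis of normal, rectal hypersensitivity, rectal hyposensitivity, or borderline hyposensitivity is made according to the London Classification disorders of rectal sensation". It puts the aim as a same-or-different question: "we aim to identify whether patients receive the same diagnosis, according to the London Classification". Section 3.3 makes the full diagnosis by each method an outcome, separately for the Laborie and the Medtronic balloon: "The London Classification diagnoses of each patient when rectal sensitivities are assessed using Laborie system elastic balloon distension versus the rectal barostat", with matching wording for Medtronic.

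Section 7.8 fixes two analyses of these data:

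- "a binary indicator will be used to determine the percentage of patients who's diagnoses were in agreement";
- as a closer look, "a Fisher's exact test will be used to determine whether the difference in number of diagnoses between the elastic balloon distension and rectal barostat" is significant, with the threshold set at 0.05.

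The section names no paired cross-tabulation, no count of changes by direction and no weighted measure of agreement. Section 3.2 has a further objective: to find which of the two balloon systems aligns better with the barostat. Section 6.3 sets 30 participants, 15 per site, and each site uses one balloon system.

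**The concern.** The four diagnoses have a natural order along the sensory-threshold scale: hypersensitive, normal, borderline hyposensitive, hyposensitive. The protocol does not state this order, but its content implies it. Sensitivity is read from the volumes at which sensations are reported, borderline hyposensitivity is by name a milder form of hyposensitivity, and the Background ties the two extremes to largely opposite complaints.

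A binary score gives a normal/borderline pair the same weight as a hypersensitive/hyposensitive pair, and it pools movement in both directions. The Fisher test compares the category totals of the two devices as if they came from separate patients, and it treats the categories as unordered. Movements that cancel in the totals leave no trace.

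Alignment with the barostat is a matter of degree. Two balloon systems could show the same percentage agreement while one misses by a single category and the other reverses the diagnosis. The designers of the definitive study would want to know which, and whether the balloon calls hypersensitivity more or less often than the barostat.

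**Working it through.** **Inputs from the protocol.** Four diagnoses (1.0); 30 patients, 15 per site (6.3); significance level 0.05, sidedness not stated (7.8). The protocol gives no expected agreement, effect size, power or barostat distribution, so there is no figure of its own to reproduce. All tables and power figures below are assumed for illustration.

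**Step 1: four assumed paired tables, n=30.** Each has 20 patients who agree (6 hypersensitive, 10 normal, 2 borderline, 2 hyposensitive) and 10 who differ. Agreement is 20/30 = 66.7% in all four.

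| Table | The 10 discordant patients | Balloon totals | Barostat totals | Fisher p (2x4) | Linear weighted kappa | Sign test p |
|---|---|---|---|---|---|---|
| A | hyper/normal, 5 each way | 11/15/2/2 | 11/15/2/2 | 1.00 | 0.59 | 1.00 |
| B | hyper/hypo, 5 each way | 11/10/2/7 | 11/10/2/7 | 1.00 | 0.20 | 1.00 |
| C | all hyper to normal | 16/10/2/2 | 6/20/2/2 | 0.028 | 0.62 | 0.002 |
| D | all hyper to hypo | 16/10/2/2 | 6/10/2/12 | 0.005 | 0.29 | 0.002 |

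Totals are in the order hypersensitive/normal/borderline/hyposensitive.

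**Step 2: weighted kappa.** kappa = 1 − (sum of weight × observed count)/(sum of weight × expected count), with weight = steps apart/3 and expected count = row total × column total/30.

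- A: observed 10 × 1/3 = 3.33. Expected 2 × (165+44+66+30+60+4)/90 = 8.20. kappa = 1 − 3.33/8.20 = 0.59.
- B: observed 10 × 1 = 10. Expected 2 × (110+44+231+20+140+14)/90 = 12.42. kappa = 1 − 10/12.42 = 0.20.

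Unweighted kappa is 0.45 for A and 0.52 for B, so it ranks the reversals as the better agreement. Chance correction alone does not repair the measure.

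**Step 3: sign test.** With all discordant patients moving one way, two-sided p = 2 × 0.5^d. For d=10 this is 0.002. For five of five at one site it is 2 × 0.5^5 = 0.0625; the Fisher test on the same 15 patients (8/5/1/1 versus 3/10/1/1) gives 0.25. At one site at least six changes, all in one direction, are needed to pass 0.05 (2 × 0.5^6 = 0.031).

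**Step 4: reading the table.**

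- A against B: neither planned analysis separates small changes from reversals.
- A against C: the percentage does not show direction, but the totals behind the Fisher test do.

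**Step 5: illustrative power, both sites pooled, two-sided 5%.** Assume a bivariate normal latent sensitivity, a barostat shift of 0.5 SD in the same direction at both sites, and latent correlation 0.5 to 0.85. The site mixes take 91.4% normal and 65.7% hypersensitive from section 2.0, with the rest assumed (3/91.4/2.8/2.8% and 65.7/28.3/3/3%). The more even mix (25/45/15/15%) is wholly assumed.

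| Mix | Planned Fisher test | Paired sign test on direction |
|---|---|---|
| Site mixes | about 4 to 7% | 30 to 48% |
| Even mix | about 13 to 21% | 54 to 89% |

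With the site mixes and correlation 0.7, this shift lowers mean agreement from 79% to 71%, that is 0.08 × 30 = 2.4 patients.

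**Step 6: precision.** The exact 95% interval for agreement is 47% to 83% for 20/30, and 38% to 88% for 10/15.

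**The case against.** **The percentage answers the stated question.** The Background asks whether the diagnosis is the same, and that is yes or no for each patient. This stands: the percentage is incomplete, not wrong, and should stay as the headline.

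**Direction is not wholly lost.** A reader might infer from the binary score that the study cannot show whether one device calls hypersensitivity more often. The documents do not support that. The per-device totals behind the Fisher test show a net shift (table C, p=0.028), and section 3.3 records every patient's diagnosis by each method. What is missing from the named analyses is the patient-level movement.

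**The site difference is not evidence of a balloon-versus-barostat shift.** Section 2.0 says of it "This suggests a possible difference in how each piece of equipment classifies patients", but it compares two balloon systems in different cohorts without a barostat, and the protocol acknowledges the cohort limitation. This stands. Shifts may differ by site: under the same model, a pooled test on step size has power of 14 to 23% if only CDDFT shifts, and about 7% if the sites shift in opposite directions.

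**Full reversals may be rare.** Under the site mixes, three-step changes are expected in 0.0 to 0.4 of 30 patients. This stands for that scenario. Most of the gain in power comes from using direction within pairs rather than step size, so the test proposed needs no category spacing.

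**A feasibility study makes no power claim, and a SAP may add detail.** Power is indeed a secondary argument here. But section 7.8 names its methods, so they can be judged as written.

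**Conclusion.** The point holds in a limited form. The percentage says nothing about the size or direction of a disagreement. The Fisher test recovers only a net shift in the totals, without pairing or order. Results as different as one-step noise and balanced reversals can therefore give identical output from both planned analyses (66.7% and p=1.00), while linearly weighted kappa is 0.59 and 0.20. This weakens the objective of comparing how well each balloon system aligns with the barostat.

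It does not make percentage agreement invalid, and no data are lost. The contrast between tables A and B rests only on accepting the order of the categories. The power figures rest on an assumed barostat distribution and a common shift at both sites, so they indicate a tendency and not a forecast. With 15 patients per site, any of these analyses yields estimates for planning rather than confirmation. The change is advisable rather than essential.

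**What to change.** Amend section 7.8 as follows:

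1. Keep percentage agreement as the descriptive headline, with an exact confidence interval, for each balloon system.
2. State the order hypersensitive < normal < borderline hyposensitive < hyposensitive.
3. Report the paired 4x4 table, balloon by barostat, separately for Laborie and Medtronic. Give the number of patients moved towards hypersensitivity and towards hyposensitivity, by one, two or three steps.
4. Replace the Fisher test with an exact paired two-sided sign test on direction of change, by site because shifts may differ between systems.
5. If a coefficient is reported, use weighted kappa with weights stated in advance and a confidence interval.

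The cost is wording only; section 3.3 already collects the diagnoses. The downsides are that the plan must commit to the order, the kappa weights are a convention, and the by-site sign test will often be inconclusive (five of five changes in one direction gives p=0.06).

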3.2 Secondary Objectives

- To assess whether they are any differences in rectal sensitivity diagnoses when using the London classification between the two methodologies (elastic balloon distension test and rectal Barostat test).
- To assess the repeatability of the rectal barostat test.
- To investigate whether patients with larger rectums require the elastic balloon to be inflated to a larger volume, before they feel an urge to defecate.
- To determine whether the Laborie elastic balloon test or Medtronic elastic balloon test aligns better with the rectal barostat test.
- To assess study participant eligibility, uptake and drop-out rate.
- To assess study acceptability and tolerability.
- To assess the costs per study of the two methodologies to help inform a definitive study (clinic time, analysis time and consumables).

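### Diagnostic agreement is summarised only as a raw percentage, which depends on the diagnosis mix on both tests and cannot by itself show agreement beyond chance or rank Laborie against Medtronic

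*Protocol*

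**What the plan says.** Section 7.8 (Data Analysis) fixes the agreement measure: "a binary indicator will be used to determine the percentage of patients" whose diagnoses on the two tests match. It adds that "a Fisher's exact test will be used to determine whether the difference in number of diagnoses" between balloon and barostat "reaches a significance level of p=0.05". No chance-corrected index and no cross-table is named.

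Section 3.2 lists as a separate objective: "To determine whether the Laborie elastic balloon test or Medtronic elastic balloon test aligns better with the rectal barostat test". Section 7.8 gives no analysis specific to it.

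Sections 5.0 and 7.5.3 tie each system to one site: Laborie at NUTH, Medtronic at CDDFT, and each patient is tested only where identified. Section 6.3 plans 15 patients per site. Section 1.0 defines four diagnoses: normal, hypersensitive, hyposensitive and borderline hyposensitive.

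Section 2.0 reports a service evaluation with 70 patients per site: "In NUTH, the majority of patients (91.4%) were diagnosed as normal, whereas in CDDFT, the majority of patients (65.7%) were diagnosed with rectal hypersensitivity". It reads this as a possible equipment difference and lists the different cohorts as a limitation.

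**The concern.** Two tests that both place most patients in the same category will match often even if they carry no shared information about the individual patient. How often depends on the shares each test gives to each diagnosis. The balloon shares at the two sites are very different, and the only agreement statistic the protocol names moves with those shares.

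Fisher's test does not fill the gap. Applied to numbers of diagnoses it compares totals between the methods. Totals can be identical while individual patients are classified differently, so it neither measures within-patient agreement nor corrects for chance.

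At stake are two readings of the results: a high percentage taken as evidence that the balloon reproduces the barostat diagnosis, and a difference in percentage between sites taken as evidence about the two systems. Either could carry over into planning the definitive study.

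**Working it through.** The protocol states no agreement target, so there is no figure of its own to reproduce. The service-evaluation percentages do correspond to whole counts: 64/70 = 91.4% and 46/70 = 65.7%.

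**Inputs**
- NUTH balloon: 64/70 normal, 6/70 not normal (section 2.0).
- CDDFT balloon: 46/70 hypersensitive, 24/70 other (section 2.0).
- 15 patients per site (section 6.3).
- Assumptions: the barostat shares, and how the remaining 6/70 and 24/70 split. Neither is given, so both are varied.

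**Formulas.** Chance agreement Pe = sum over diagnoses of (balloon share × barostat share). Kappa = (Po − Pe)/(1 − Pe), where Po is the raw agreement.

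**1. Barostat shares equal to balloon shares at each site, tests unrelated**
- NUTH, remainder in one category: (64/70)² + (6/70)² = 4132/4900 = 0.843. Remainder split equally in three: (64/70)² + 3(2/70)² = 4108/4900 = 0.838.
- CDDFT, remainder in one category: (46/70)² + (24/70)² = 2692/4900 = 0.549. Split equally in three: (46/70)² + 3(8/70)² = 2308/4900 = 0.471.
- Gap: 0.843 − 0.549 = 0.29, up to 0.838 − 0.471 = 0.37.

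With two independent Binomial(15, p) counts, NUTH shows the higher raw agreement with probability about 0.95 to 0.98 over these splits.

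The gap shrinks but remains if the tests are related to the same degree at both sites. From Po = Pe + kappa × (1 − Pe), with Pe 0.843 and 0.549:

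| True kappa at both sites | NUTH raw | CDDFT raw |
|---|---|---|
| 0.4 | 90.6% | 73.0% |
| 0.6 | 93.7% | 82.0% |

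**2. One common barostat distribution at both sites, tests unrelated.** Use normal and hypersensitive only, with barostat share normal q.
- NUTH: Pe = q(64/70) + (1 − q)(6/70).
- CDDFT: Pe = q(24/70) + (1 − q)(46/70).
- Difference: (2q − 1)(40/70), which is zero at q = 0.5.

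| q | NUTH | CDDFT |
|---|---|---|
| 91.4% | 84% | 37% |
| 70% | 67% | 44% |
| 50% | 50% | 50% |
| 34.3% | 37% | 55% |
| 20% | 25% | 59% |

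The crossing point moves somewhat with the split of the remainder. With 12/70 normal and 12/70 hyposensitive or borderline at CDDFT it is where 52q = 40(1 − q), that is q = 40/92 = 43%.

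**3. The same raw percentage with different meaning.** Take 13 matches in 15 (86.7%) at each site.
- Each test calls 14 of 15 normal and they disagree on who is abnormal (table 13/1/1/0): Pe = (14/15)² + (1/15)² = 197/225; kappa = (195 − 197)/(225 − 197) = −0.07.
- Each test calls 10 hypersensitive and 5 normal (table 4/1/1/9): Pe = (10/15)² + (5/15)² = 125/225; kappa = (195 − 125)/(225 − 125) = 0.70.

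**4. Little information on abnormal diagnoses at NUTH.** At the service-evaluation share, the expected number not normal on the balloon is 15 × 6/70 = 1.3, and the probability of none is (64/70)^15 = 0.26.

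**5. Kappa also depends on mix.** Suppose both systems had sensitivity and specificity 0.8 against the barostat, with two categories. Raw agreement is 80% whatever the mix.
- Barostat abnormal 8.6%: balloon abnormal 0.8 × 0.086 + 0.2 × 0.914 = 0.251; Pe = 0.706; kappa = 0.094/0.294 = 0.32.
- Barostat abnormal 65.7%: balloon abnormal 0.8 × 0.657 + 0.2 × 0.343 = 0.594; Pe = 0.530; kappa = 0.270/0.470 = 0.57.

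**The case against.** The strongest reply is that percentage agreement directly answers the question in section 1.0, whether a patient receives the same diagnosis from either test, and that section 7.8 never says it will be used to rank the systems. This is a 30-patient feasibility study, the outcome is secondary, and extra coefficients are often left to a SAP. In part this stands: the percentage is a legitimate summary and should stay. But 7.8 does fix the measure, and names nothing else for the section 3.2 comparison.

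A second reply is that unrelated tests are an extreme case, since both tests assess rectal sensation in the same patient at one appointment. That is fair. The 29-to-37-point gap is the chance component under stated assumptions and does not predict the result. At equal kappa of 0.4 or 0.6 the gap is about 18 or 12 points, and at equal sensitivity and specificity of 0.8 there is none. (That last case is illustrative: it implies 25% abnormal on the NUTH balloon, against 8.6% in the service evaluation.)

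A reader might infer that NUTH is bound to look better aligned whatever the device does. The documents do not support that. It needs the barostat also to call most NUTH patients normal, and no barostat distribution is given; step 2 shows that the direction can reverse. Nor is it established that nearly all NUTH patients are normal or that the sites differ in case mix. The 91.4% and 65.7% are outputs of two balloon systems which, by section 1.0, use different published normal ranges. If the systems cause the gap, a mismatch with the barostat at one site is part of the signal that section 3.2 seeks.

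It is also fair to say that kappa is no cure by itself, as step 5 shows.

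**Conclusion.** The point holds in conditional form. As the only stated agreement measure, the raw percentage cannot show agreement beyond chance and cannot on its own rank Laborie against Medtronic. Its chance component could be about 84% at NUTH and 47-55% at CDDFT if barostat shares resemble the service-evaluation balloon shares. It could equally favour neither site, or CDDFT, if the barostat calls half or fewer of patients normal at both sites (two-category case). These sizes rest on assumed barostat shares and on unrelated tests. The conclusion that the percentage depends on mix and needs the cross-table beside it does not rest on any one scenario.

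No coefficient removes the confounding of system with site and patient mix, so the by-site results can only be descriptive. This is an inexpensive improvement that should be made; it does not invalidate the study.

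**What to change.** In section 7.8:
- Keep percentage agreement, with an exact 95% CI.
- Add, by site, the full 4x4 balloon-by-barostat table and category-specific agreement.
- Add, by site, kappa together with a prevalence-robust index such as Gwet's AC1, each with a 95% CI.
- State that the two systems will not be ranked on the raw percentage or on any single coefficient, because each is used at one site only and device is confounded with site and patient mix. Describe the by-site results as descriptive.

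The cost is a few lines of text and analysis on data already collected. The drawback is imprecision. At 13 of 15 matches the exact 95% CI, from solving P(X ≥ 13) = 0.025 and P(X ≤ 13) = 0.025 for a Binomial(15, p), runs from 60% to 98%. Kappa will also be imprecise at this size, and may be undefined at a site where both tests call every patient normal. The intervals must therefore be shown with the estimates.

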6.3 Number of Participants

In total 30 participants will be recruited for the study. 15 participants will be recruited at NuTH and 15 at CDDFT. Study recruitment will continue until complete study data has been obtained from 15 participants at each site.

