7.4 Randomisation

All participants will have the rectal barostat test, but the order of tests will be changed per patient to avoid bias on the order of tests influencing the results. Patients will either receive procedure A or procedure B:

- Procedure A: Anorectal manometry, elastic balloon distension, endoanal ultrasound, rectal barostat
- **Procedure B**: Rectal barostat, endoanal ultrasound, anorectal manometry, elastic balloon distension

The basic details (e.g. short title, study overview) of the study will be registered with the online randomisation software, Sealed Envelope (https://www.sealedenvelope.com/). The simple randomisation service for non-commercial clinical studies will be selected. At each site a secure NHS email address accessible only to the research team will be used to perform each randomisation. The unique participant randomisation number will be entered into the software. The software will then automatically randomise to procedure A or procedure B. A copy of the randomisation is also automatically emailed. The email containing the randomisation allocation will be printed out and saved as part of the SIF.

Randomisation will occur once informed consent has been obtained and the study eligibility of the participant has been confirmed.

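### Section 7.8 fixes Fisher's exact test, an independent-groups test, for diagnoses that are paired within patient

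*Protocol*

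**What the plan says.** The design is within-patient. Section 1.0 says "patients attending for their standard rectal sensitivity tests using the elastic balloon will be invited to repeat their study using the rectal barostat", and section 7.4 says "All participants will have the rectal barostat test, but the order of tests will be changed per patient". Only the order is randomised. With each test, "a diagnosis of normal, rectal hypersensitivity, rectal hyposensitivity, or borderline hyposensitivity is made" (section 1.0), so each participant ends with two diagnoses on the same four-category scale.

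Section 6.3 sets the size: "In total 30 participants will be recruited for the study", and "15 participants will be recruited at NuTH and 15 at CDDFT". The sites use different balloon systems (Laborie at NUTH, Medtronic at CDDFT). Section 3.3 defines the diagnosis outcome separately for each system against the barostat.

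Section 7.8 plans two steps. First, "a binary indicator will be used to determine the percentage of patients who's diagnoses were in agreement". Then, as a closer look, "a Fisher's exact test will be used to determine whether the difference in number of diagnoses between the elastic balloon distension and rectal barostat", judged against a threshold of 0.05. It does not give the layout of the Fisher table, and it names no paired test for the diagnoses.

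**The concern.** Fisher's exact test compares proportions between two groups of different people. Here the same people appear on both sides. There are two ways to lay out the table, and neither suits the question.

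- **Totals by method.** This is what a difference in the number of diagnoses between methods most naturally means. The 30 patients enter as 60 results treated as independent, and the record of who changed diagnosis is lost.
- **Patient-level cross-table (balloon by barostat).** The 30 patients enter once each, but Fisher then tests whether the two diagnoses are associated. Strong association is compatible with full agreement and with full disagreement.

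Agreement in London diagnoses is the question in the study title and the first secondary objective, and section 2.0 says the results will inform a definitive study of the same question. A non-significant Fisher result could be taken as support for the methods being equivalent, and section 4.0 describes the study in equivalence terms. Planning the next study also needs the rate of discordant pairs, which the totals discard.

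**Working it through.** **Inputs.** From the protocol: n=30 pairs, 15 per balloon system, alpha 0.05 (two-sided assumed, since sidedness is not stated). The protocol gives no effect size, discordance rate or power for this comparison, so there is no figure to reproduce. All cell values below are assumptions. For the examples the four diagnoses are reduced to two (for instance hypersensitive or not).

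**Notation.** For each pair, a = positive on both methods, b = positive on the balloon only, c = positive on the barostat only, d = positive on neither.
- Fisher on totals uses the table [a+b, c+d; a+c, b+d].
- Exact McNemar uses only the discordant pairs: two-sided binomial of b out of b+c at 0.5.

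**1. A one-way shift.** Suppose 8 of 30 patients all change from normal to hypersensitive, so normal/hypersensitive goes from 20/10 to 12/18.
- Fisher on [20, 10; 12, 18]: p=0.069.
- Exact McNemar, 8 of 8 one way: p = 2 x 0.5^8 = 0.008.

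**2. Why the error rate is wrong.** Write the cells as probabilities. The difference between the two proportions has variance [(b+c) - (b-c)^2]/n when paired. An independent-groups test takes it as [p1(1-p1) + p2(1-p2)]/n.
- No shift, 30% discordant, cells (0.35, 0.15, 0.15, 0.35): paired 0.30/30 = 0.0100; treated as independent 0.50/30 = 0.0167. The test is too cautious. By full enumeration at n=30 it rejects 0.46% of the time, against 2.1% for exact McNemar.
- No shift, all pairs discordant, cells (0, 0.5, 0.5, 0): paired 1.00/30 = 0.0333; treated as independent 0.0167. The test is now too liberal: it rejects 9.9%, against 4.3% for exact McNemar.

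Positive correlation within patients is the more plausible case, so the likely error is on the cautious side.

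**3. Power for an assumed 25-point shift.** Take 37% to 62% with 3% reverse discordance, that is cells (0.34, 0.03, 0.28, 0.35). Full enumeration gives:

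| n | Fisher on totals | Exact McNemar |
|---|---|---|
| 30 (pooled) | 35% | 64% |
| 15 (one system) | 8% | 16% |

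With 25% one-way discordance, none reverse and 30% positive on both, the n=30 figures are 34% and 80%.

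**4. What Fisher on totals can and cannot see (n=30).**
- With 9 or more changes, all one way, p is at most 0.038 whatever the concordant pairs are.
- With 6 changes, all one way, exact McNemar gives p=0.031. Fisher gives 0.024 for (0, 6, 0, 24) but 0.187 for (9, 6, 0, 15), so it depends on patients who did not change.
- With 15 changes each way, (0, 15, 15, 0), agreement is 0%. Fisher gives p=1.00, and so does exact McNemar.

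**5. The cross-table reading.** Fisher gives p<0.001 for complete agreement (15, 0, 0, 15) and p<0.001 for complete disagreement (0, 15, 15, 0). It cannot tell them apart.

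**The case against.** The strongest reply is that section 7.8 already answers the main question correctly. The percentage of patients in agreement is a paired, per-patient summary, and Fisher is only an addition to it. The study has no primary outcome measure, and no power claim or progression rule rests on this p-value. That stands, and it limits the severity.

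A reader might infer more than the documents support:

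- **That the test cannot detect disagreement at all.** It can detect a large one-way shift (step 4). It misses balanced disagreement, but so does McNemar. The 15-each-way case therefore shows that tests of marginal shift do not measure agreement. It does not show that Fisher is worse than a paired test there. Only the percentage agreement exposes that case.
- **That the plan definitely counts 30 patients as 60.** This is the natural reading of the wording, not a stated layout. The other layout fails for a different reason.
- **That the planned agreement figure is itself wrong.** It is calculated validly. The lack of an interval or chance correction could be left to an analysis plan that is not shown.
- **That chance agreement is about 84%.** That takes the NUTH mix in section 2.0 for both methods: 0.914^2 + 0.086^2 = 0.843. The CDDFT figure gives 0.657^2 + 0.343^2 = 0.549. Both sums put all other diagnoses into one class and assume the barostat has the same mix, for which the protocol gives no data.

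It is also fair to say that exact McNemar is conservative here (2.1% at a nominal 5%) and that, at 15 per system, changing the test rescues little.

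**Conclusion.** The stated analysis is wrong and should be fixed. This is a named test that does not match the design, not a detail left for later. On the totals reading it discards the pairing, rejects about 0.5% of the time at a nominal 5% under 30% balanced discordance, and has roughly half the power of a paired test for the assumed 25-point shift (35% against 64% at n=30). On the cross-table reading it tests association.

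The mismatch between test and design follows from the protocol alone. The sizes rest on assumed cell values, a two-category reduction and two-sided testing. The consequence is moderate: a secondary outcome of a feasibility study, with a valid percentage agreement beside it and an error that is probably conservative. The practical risk is a non-significant result read as reassurance.

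**What to change.** In section 7.8:

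1. Delete the Fisher sentence.
2. Keep percentage agreement as the main summary. Add an exact 95% CI and the paired 4x4 table of balloon by barostat diagnosis.
3. Add kappa with a CI as a supportive measure. Weight it only if an ordering of the four diagnoses is justified; section 1.0 lists them without ordering them.
4. If a test of shift between methods is kept, use exact McNemar on a stated split (for example hypersensitive versus not), or Bowker/Stuart-Maxwell where the table is not too sparse. Say that it tests shift, not agreement.
5. Report by balloon system, as section 3.3 defines the outcome, and pooled. State that at 15 per system any test has little power, so that estimates with intervals lead.

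The cost is a short change of wording and a few lines of analysis code. No extra patients or data are needed.
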